The timeframe of first visit of the ZOSTER-073 study in LTFU phase will be computed between the date of the first visit of ZOSTER-073 study and the administration date of the second dose of primary series vaccination in the ZOSTER-041 study.

Time frame of first visit= (date of the first visit of ZOSTER-073 - date of vaccination dose 2 in ZOSTER-041+1) /365

The result of the first visit will be assigned to each yearly timeframe derived as follow

Timeframe of first visit	Lower bound of timeframe of first visit	Upper bound of timeframe of first visit
4	[3.5	<4.5)
5	[4.5	<5.5)
6	[5.5	<6.5)

The brackets indicate inclusive.

Yearly timeframe for the persistence analysis in the LTFU phase will be calculated by adding 1 year to the timeframe of first visit for each subsequent visit.

Example

	Primary series dose 2 – ZOSTER-041	Day 1- ZOSTER-073 Blood sample	time since primary series dose 2	assigned time frame for the ZOSTER-073 Visit 1 Day 1 blood sample	assigned time frame for the ZOSTER-073 Visit 2 blood sample	assigned time frame for the ZOSTER-073 Visit 3 blood sample
subject 1	1-nov-11	2-feb-16	4.260273973	4	5	6
subject 2	1-nov-11	5-jul-16	4.682191781	5	6	7

Similar computations will be performed for ZOSTER-073 Visit 6 and Visit 7 for non-revaccinated subjects.

Since pre-revaccination visits encompass a broad time range post-dose 2 of the primary series, the same interval may include one subject's data from ZOSTER-073 Visit 1 and another subject's Visit 2 data due to overlapping in timepoints by study year associated with the long-term follow-up phase.

Timepoints from ZOSTER-041 will be displayed in the immunogenicity summaries for both the LTFU phase and revaccination active and follow-up phases.

The following visits will appear in the immunogenicity summaries for the Per Protocol Set for analysis of persistence (LTFU phase). ZOSTER-041 Visits 1-5 and ZOSTER-073 Visits 1-3 will include data from both revaccinated and non-revaccinated subjects (prior to revaccination). ZOSTER-073 Visit 6 and Visit 7 will include data from non-revaccinated subjects only.

Study Phase	Subjects	Visit Number	SDTM.IS Visit Number	Study Month	Display	Description
ZOSTER-041	Revaccinated and Non-revaccinated	Visit 1	10	Month 0	PRE	Pre-vaccination (Month 0)
		Visit 2	20	Month 1	PI(M1)	Post-vaccination dose 1 (Month 1) – 1 month post-dose 1 ZOSTER-041

		Visit 3	30	Month 2	PII(M2)	Post-vaccination dose 2 (Month 2) – 1 month post-dose 2 ZOSTER-041

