3. ANALYSIS SETS

Analysis Set	Description
Enrolled Set	All subjects with a complete vaccination course (2 doses of HZ/su vaccine) in study ZOSTER-041 who met the eligibility criteria and signed informed consent in the study ZOSTER-073.
Per Protocol Set (PPS) for analysis of persistence (LTFU phase from Visit 1 to Visit 3 for all subjects, and at Visit 6 and Visit 7 for non-revaccinated subjects)	The PPS for analysis of persistence will include evaluable subjects (i.e. those meeting all eligibility criteria, complying with the procedures and intervals defined in the protocol, with no elimination criteria) from the Enrolled Set for whom any persistence immunogenicity endpoints measures after primary vaccination course are available from Visit 1 (Day 1) to Visit 3 (study Month 24) regardless of revaccination status and at Visit 6 (study Month 37) and/or Visit 7 (study Month 49) for non-revaccinated subjects.
Exposed Set (ES) for revaccination phase	The ES for analysis of safety will include all subjects with at least one HZ/su vaccine dose administered in the study ZOSTER-073.
PPS for Immunogenicity after revaccination course (revaccination active phase)	The PPS for analysis of immunogenicity after revaccination will be defined by time-point and will include evaluable subjects (i.e. those meeting all eligibility criteria, complying with the procedures and intervals defined in the protocol, with no elimination criteria) from the ES for revaccination who have received 1 or 2 doses of revaccination up to the time point considered from Visit 3 (study Month 24) to Visit 5 (study Month 26) (i.e. 1 dose for Visit 4 and 2 doses for Visit 5) and have any immunogenicity endpoint measures available.
PPS for persistence after revaccination course (revaccination follow-up phase)	The PPS for persistence for analysis of immunogenicity after revaccination will include evaluable subjects (i.e. those meeting all eligibility criteria, complying with the procedures and intervals defined in the protocol, with no elimination criteria) from the ES for revaccination who received 2 doses of revaccination for whom persistence immunogenicity endpoints measures after revaccination course are available with any immunogenicity endpoint measures available from Visit 6 (study Month 37) to Visit 7 (study Month 49).

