4.2. Primary Endpoints Analyses

The primary immunogenicity analysis for the LTFU phase will be performed using the PPS for analysis of persistence (LTFU phase from Visit 1 to Visit 3 for all subjects, and at Visit 6 and Visit 7 for non-revaccinated subjects). If 5% subjects or more with serological results are eliminated from the PPS for analysis of persistence, then a complementary analysis will be performed on the Enrolled Set.

The primary immunogenicity analysis for the revaccination active phase will be performed on the PPS for immunogenicity after revaccination course (revaccination active phase). If 5% subjects or more with serological results are eliminated from the PPS for revaccination active phase, then a complementary analysis will be performed on the Exposed Set.

All analyses will be performed overall.

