4.2.2. Main analytical approach

4.2.2.1. Long-term follow-up phase

For persistence of humoral immunity measured after the primary vaccination course, the following parameters will be tabulated. ZOSTER-073 Day 1, study Month 12 and study Month 24 measurements will be displayed in tables and figures in terms of time since primary series in ZOSTER-041, grouped into 1 year intervals.

- GMCs of anti-gE antibody, MGI of post-vaccination timepoint over ZOSTER-041 pre-vaccination timepoint, and anti-gE antibody seropositivity rates with 95% CI;
 - GMCs of anti-gE antibody, MGI of post-vaccination timepoint over ZOSTER-041 pre-vaccination timepoint, and anti-gE antibody seropositivity rates with 95% CI will also be presented with Visit 1, Visit 2, and Visit 3 in the LTFU phase of ZOSTER-073 presented as Day 1, Month 12, and Month 24, in accordance to the primary endpoint timepoints.

- Descriptive statistics on anti-gE antibody concentrations (mean, SD, min, Q1, median, Q3, max);
- Vaccine response rates and 95% CIs to ZOSTER-041 pre-primary vaccination for anti-gE antibody concentrations;
- Descriptive statistics of the fold increase of post-vaccination timepoint over ZOSTER-041 pre-vaccination timepoint at ZOSTER-073 Day 1, study Month 12, and study Month 24 (mean, SD, min, Q1, median, Q3, max);
- Distribution of the fold over ZOSTER-041 pre-vaccination timepoint;
- The distribution of antibody titers will be tabulated and also presented using reverse cumulative curves.

Displays of GMCs of anti-gE antibody concentrations will also include all of the ZOSTER-041 timepoints.

Anti-gE antibody concentrations will be displayed graphically by time since primary vaccination dose 2. Values taken pre-primary vaccination, at 1 month post primary vaccination dose-1, and timepoints post-dose 2 of primary vaccination will be presented in separate symbols and colors in the figure, along with a trend line through post-dose 2 points. A line representing the median pre-vaccination concentration will be displayed for comparison.

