4.3.1.2.3. Revaccination follow-up phase

For **humoral immunity** after revaccination (revaccination follow-up phase), the following parameters will be tabulated. ZOSTER-073 study Months 37 and 49 (Visit 6 and Visit 7) data will be presented in terms of time since revaccination, grouped in appropriate month intervals, based on the distribution subjects' visit occurrence. For non-revaccinated subjects, separate summaries will be provided, and data will be presented on time since primary vaccination in ZOSTER-041.

- GMC of anti-gE antibody and anti-gE seropositivity rates with 95%;
- Vaccine response rates for anti-gE antibody concentrations over pre-revaccination timepoint with 95% CI;
- Vaccine response rates to ZOSTER-041 pre-primary vaccination for anti-gE antibody concentrations with 95% CI;
- MGI post-revaccination over pre-revaccination timepoint with 95% CI;
- MGI post-revaccination over ZOSTER-041 pre-vaccination timepoint with 95% CI
- MGI post-revaccination dose 1 over 1 month post primary vaccination dose 2 with 95% CI
- Descriptive statistics of the fold increase of anti-gE antibody concentrations over pre-revaccination timepoint (mean, standard deviation, min, Q1, median, Q3, max).

- Descriptive statistics of the fold increase of anti-gE antibody concentrations over ZOSTER-041 pre-vaccination timepoint (mean, SD, min, Q1, median, Q3, max).
- Distribution of antibody titers will be tabulated and also presented using reverse cumulative curves.
- Boxplots of anti-gE antibody concentrations will be displayed by visit.

For **cellular immunity** after revaccination (revaccination follow-up phase) as determined by ICS, the following parameters will be tabulated. ZOSTER-073 study Months 37 and 49 (Visit 6 and Visit 7) data will be presented in terms of time since revaccination, grouped in appropriate month intervals, based on the distribution subjects' visit occurrence. For non-revaccinated subjects, separate summaries will be provided, and data will be presented on time since primary vaccination in ZOSTER-041.

- Descriptive statistics (N, mean, SD, min, Q1, median, Q3, max):
 - the frequency of gE specific CD4+T-cells secreting at least 2 activation markers (among IFN- γ , IL-2, TNF- α , CD40L);
 - the fold increase over pre-revaccination timepoint in the frequency of gE specific CD4[2+] T-cells.

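### In the SAP's yearly persistence displays, years 7 and 8 mix all subjects with the late visits of non-revaccinated subjects, and years 9 and 10 come from non-revaccinated subjects alone

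*SAP*

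**What the plan says.** SAP Section 4.2 runs the primary long-term follow-up (LTFU) analysis on a per-protocol set described as "LTFU phase from Visit 1 to Visit 3 for all subjects, and at Visit 6 and Visit 7 for non-revaccinated subjects". Section 3 defines the set the same way, adding measures "at Visit 6 (study Month 37) and/or Visit 7 (study Month 49) for non-revaccinated subjects".

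Section 1.2 lists the visits that appear in the immunogenicity summaries for this set and notes that "ZOSTER-073 Visit 6 and Visit 7 will include data from non-revaccinated subjects only". It labels every LTFU visit by year since dose 2 of the primary series. The first visit is assigned to year 4, 5 or 6, and later years are "calculated by adding 1 year to the timeframe of first visit for each subsequent visit". For the extension, "Similar computations will be performed for ZOSTER-073 Visit 6 and Visit 7 for non-revaccinated subjects". The SAP accepts that "the same interval may include one subject's data from ZOSTER-073 Visit 1 and another subject's Visit 2 data".

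Section 4.2.2.1 puts the tables and figures on this yearly scale and plots concentrations "along with a trend line through post-dose 2 points". Plot symbols separate pre-vaccination, post-dose 1 and post-dose 2 values, but not revaccination status.

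Three other provisions bear on the point:
- Sections 1.2 and 4.2.2.1 also present Visits 1 to 3 as Day 1, Month 12 and Month 24. Section 4.2.2.1 names GMC, MGI and seropositivity for this.
- Section 4.3.1.2.3 says of Visits 6 and 7: "For non-revaccinated subjects, separate summaries will be provided".
- Section 4.8 discloses that Visits 6 and 7 were added to the set. Protocol Section 10.2 had confined it to Visits 1 to 3.

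**The concern.** A yearly curve is read as one cohort followed through time. Here the population changes along the axis, and only at the late end. Non-revaccinated subjects are not a random sample: the protocol glossary defines them as ineligible or unwilling. The revaccination criteria in Protocol 6.1.2 and 6.2.2 exclude, among others, subjects with recent rejection, confirmed HZ in the preceding year, recent immunoglobulin or B-cell agents, or suspected non-adherence. Protocol 7.6 itself says that HZ and exogenous immunoglobulin confound the anti-gE measurement.

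If these subjects' antibody levels differ from the others', the late curve could show a drop, plateau or rise that reflects who was not revaccinated rather than waning of the primary response. Late persistence is what an extension study of this kind is read for.

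**Working it through.** **1. The SAP's own binning example.** The rule in Section 1.2 is (first ZOSTER-073 visit date - dose 2 date + 1)/365. From 1 Nov 2011 to 2 Feb 2016 is 1554 days: 1555/365 = 4.2603, year 4. From 1 Nov 2011 to 5 Jul 2016 is 1708 days: 1709/365 = 4.6822, year 5. Both match the SAP.

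**2. Contents of each year.** Non-revaccinated subjects have no Visits 4 and 5, so I read the rule for them as Visit 6 = first year + 3 and Visit 7 = first year + 4. An asterisk marks values from non-revaccinated subjects only.

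| Year | First visit in year 4 | First visit in year 5 | First visit in year 6 |
|---|---|---|---|
| 4 | V1 | - | - |
| 5 | V2 | V1 | - |
| 6 | V3 | V2 | V1 |
| 7 | V6* | V3 | V2 |
| 8 | V7* | V6* | V3 |
| 9 | - | V7* | V6* |
| 10 | - | - | V7* |

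Years 4 to 6 hold no late values, years 7 and 8 are mixed, and years 9 and 10 are entirely non-revaccinated. If no first visit falls in year 6, year 8 is entirely non-revaccinated too and year 10 is empty.

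**3. Share of late values.** SAP Table 1 gives 68 enrolled. The number not revaccinated and the split of first-visit years are not given. Assume an equal split (68/3 = 22.7 per first-visit year), a fraction f not revaccinated, and all visits attended. Visits 6 and 7 then supply f/(2 + f) of year 7 and 2f/(1 + 2f) of year 8.

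| f (assumed) | Year 7 | Year 8 | Values in year 9 | Values in year 10 |
|---|---|---|---|---|
| 10% | 5% | 17% | 5 | 2 |
| 20% | 9% | 29% | 9 | 5 |
| 30% | 13% | 37% | 14 | 7 |
| 50% | 20% | 50% | 23 | 11 |

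**4. Shift of the year-7 GMC.** If k added values have a GMC r times that of the n others, the pooled GMC is multiplied by r^(k/(n + k)). Take k = 10 and r from 0.5 to 2, both assumed.
- n = 30: exponent 10/40 = 0.25, factor 0.84 to 1.19, or -16% to +19%.
- n = 45: exponent 10/55 = 0.18, factor 0.88 to 1.13, or -12% to +13%.

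The second n is the step 3 figure (2 x 22.7 = 45). There, k = 10 needs 10/22.7 = 44% of the subjects with a first visit in year 4 to be non-revaccinated. With k = 4 and n = 45 the exponent is 4/49 and the factor 0.94 to 1.06.

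**5. Later years, with no true waning.** Non-revaccinated subjects also contribute to Visits 1 to 3. Their share of all values is f in year 4, 3f/(1 + 2f) in year 8, and 1 in years 9 and 10. Relative to year 4 the curve stands at r^(share - f). For f from 10% to 50%:
- r = 0.5: 0.83 to 0.90 in year 8, and 0.54 to 0.71 in years 9 and 10.
- r = 2: 1.11 to 1.20 in year 8, and 1.41 to 1.87 in years 9 and 10.

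**The case against.** **The primary endpoint is safe.** A reader might infer that the SAP has lost the protocol's endpoint of Day 1, Month 12 and Month 24 in all subjects. It has not: GMC, MGI and seropositivity with confidence intervals are tabulated at those timepoints, and Visits 6 and 7 cannot enter those tables. Section 1.2 announces the by-visit view without naming statistics, so a broad reading might cover more. Section 4.2.2.1, which specifies the outputs, names only these three.

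**The lead-in to 4.2.2.1 mentions only three visits.** It names Day 1, Month 12 and Month 24 for tables and figures, and the fold-increase item repeats them. A reader might state as fact that Visits 6 and 7 feed the trend line; the documents do not settle that. For the summaries, Section 1.2 does list Visits 6 and 7 on the yearly scale. The two sections need reconciling.

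**The change is disclosed and purposeful.** Section 4.8 says so, and unboosted late values can come only from non-revaccinated subjects. This stands. It justifies reporting the values, but not placing them unmarked in the same yearly rows. The separate summaries in 4.3.1.2.3 do not take them out of the LTFU set.

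**The selection may be mild.** Nothing in the documents links refusal to antibody level, and some exclusions (pregnancy, unsafe intramuscular injection) have no stated link either. Elimination codes 2050, 2060 and 2070 apply to the LTFU set and remove some affected values. The protection is partial: code 2060 removes only the affected visits, and code 2040 for forbidden medication does not list the LTFU set.

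**Removing Visits 6 and 7 does not make the curve homogeneous.** Year 4 would still come only from subjects with a first visit in year 4, and year 8 only from those with a first visit in year 6. That is true and limits the gain.

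**Conclusion.** The point holds for the yearly-interval displays from year 7 on. That years 7 and 8 are mixed and years 9 and 10 wholly non-revaccinated follows from the SAP's rule, given first visits in years 4, 5 and 6 and the reading of Visits 6 and 7 as +3 and +4 years. The exposed outputs are those with no unpooled version stated in 4.2.2.1: response rates, descriptive statistics, fold increases, distributions and reverse cumulative curves. Whether the trend line is affected is unclear.

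A reader might go further and conclude that the late curve is biased in a known direction or by a known amount. The documents do not support that: they give neither the number not revaccinated nor any difference in antibody level. Every percentage above is an illustration. The study is descriptive with no hypothesis test, so what is at stake is interpretation of late persistence, not a decision rule. The change is worth making because it is cheap and keeps all the data.

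**What to change.** In SAP Section 4.2.2.1, base the main yearly LTFU tables, reverse cumulative curves and trend line on Visits 1 to 3, matching the persistence set in Protocol 10.2. Show Visits 6 and 7 of non-revaccinated subjects in a separate panel, or with a distinct symbol and line, beside the same subjects' own Visit 1 to 3 values. Give n by revaccination status in each yearly interval. Align Section 1.2 with the lead-in to 4.2.2.1 so that the visits entering each table and figure are explicit.

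The cost is SAP wording, a table split and a figure legend; no new data are needed. The downsides are that the main curve ends at Visit 3 (year 8 at most), that later years appear only in the separate display, and that the yearly intervals still differ in first-visit year. Under the equal-split assumption with 68 subjects, years 7 and 8 would keep about 45 and 23 values.

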3.1. Criteria for eliminating data from analysis sets

Elimination codes are used to identify subjects to be eliminated from analysis due to various conditions.

Code	Condition under which the code is used	Analysis set eliminated from	Visit (timepoints) where the code is applicable	Type of Elimination
800	Fraudulent data	All	Visit 1 – Visit 7	Eliminate from all Visits
900	Invalid ICF	All	Visit 1 – Visit 7	Eliminate from all Visits
900	Subject and investigator signed informed consent never available on site	All	Visit 1 – Visit 7	Eliminate from all Visits
900	Wrong informed consent version signed, and never re-consented with correct version prior to revaccination	All	Visit 1 – Visit 7	Eliminate from all Visits
900	Informed consent never signed and/or dated by subject	All	Visit 1 – Visit 7	Eliminate from all Visits
900	Informed consent never signed and/or dated by appropriate site staff.	All	Visit 1 – Visit 7	Eliminate from all Visits
900	Other informed consent violation that cannot or were not corrected under GCP	All	Visit 1 – Visit 7	Eliminate from all Visits
1030	Study vaccine not re-administered	ES, PPS (revacc. active phase), PPS (revacc. follow-up phase)	Visit 3 – Visit 7	Eliminate from Visit and onwards
1040	Administration of concomitant vaccine(s) forbidden in the protocol	PPS (LTFU), PPS (revacc. active phase), PPS (revacc. follow-up phase)	Visit 1 – Visit 7	Eliminate from Visit and onwards
1070	Study vaccine administration route not according to protocol i.e., Subjects that received multiple doses at 1 visit, subjects whose route of vaccination is not IM Injection, or wrong reconstitution. Note that laterality is preferred but not required, therefore vaccine administration in non-dominant arm will be included in analysis.	PPS (revacc. active phase), PPS (revacc. follow-up phase)	Visit 3 – Visit 7	Eliminate from Visit and onwards
1080	Vaccine temperature deviation or vaccine administered despite poor Good Manufacturing Practices (GMP)	PPS (revacc. active phase), PPS (revacc. follow-up phase)	Visit 3 – Visit 7	Eliminate from Visit and onwards
1090	Expired vaccine administered to subject	PPS (revacc. active phase), PPS (revacc. follow-up phase)	Visit 3 – Visit 7	Eliminate from Visit and onwards
2010	Protocol violation (inclusion/exclusion criteria) – Ineligible subject was	PPS (revacc. active phase), PPS	Visit 3 – Visit 7	Eliminate from Visit and onwards

Code	Condition under which the code is used	Analysis set eliminated from	Visit (timepoints) where the code is applicable	Type of Elimination
	revaccinated without fulfilling the eligibility criteria for revaccination	(revacc. follow-up phase)		
2040	Administration of any concomitant medication(s) forbidden by the protocol	PPS (revacc. active phase), PPS (revacc. follow-up phase)	Visit 1 – Visit 7	Eliminate from Visit(s) only, as applicable
2050	Underlying medical condition forbidden by the protocol, or some Intercurrent medical conditions (IMCs). (To be determined before analysis during data management review (DMR))	PPS (LTFU), PPS (revacc. active phase), PPS (revacc. follow-up phase)	Visit 1 – Visit 7 (visit and onward)	Eliminate from Visit and onwards
2060	Concomitant infection related to the revaccination which may influence immune response – For example, clinically diagnosed suspected HZ cases before Visit 1 or PCR confirmed HZ cases after Visit 1	PPS (LTFU), PPS (revacc. active phase), PPS (revacc. follow-up phase)	Visit 1 – Visit 7	Eliminate from Visit(s) only, as applicable
2070	Concomitant infection not related to the vaccine which may influence immune response – For example, in case of revaccination, any additional confirmed or suspected immunosuppressive or immunodeficient condition (e.g., malignancy, hepatitis, HIV infection, systemic infection)	PPS (LTFU), PPS (revacc. active phase), PPS (revacc. follow-up phase)	Visit 1 – Visit 7	Eliminate from Visit and onwards
2080	Out of window treatment administration – Revaccination dose 1 (study Month 24) to revaccination dose 2 (study Month 25) outside 25-90 day interval	PPS (revacc. active phase), PPS (revacc. follow-up phase)	Visit 3 – Visit 4	Eliminate from Visit and onwards
2090	Missed Visit, excluding phone contact Note: this does not apply to delayed enrolled subjects who had their Visit 1 and Visit 2 on the same day.	PPS (LTFU), PPS (revacc. active phase), PPS (revacc. follow-up phase)	Visit 1 – Visit 7	Eliminate from Visit only
2090	Assessment not properly performed – For example, incomplete assessment, missed assessment except safety follow-up Note: this does not apply to delayed enrolled subjects who had their Visit 1 and Visit 2 on the same day. These subjects would have to have an assessment at either Visit 1 or Visit 2.	PPS (LTFU), PPS (revacc. active phase), PPS (revacc. follow-up phase)	Visit 1 – Visit 7	Eliminate from Visit only

Code	Condition under which the code is used	Analysis set eliminated from	Visit (timepoints) where the code is applicable	Type of Elimination
2090	Number of days between Visit 3 and Visit 4 blood sample is outside [25-90 days]	PPS (revacc. active phase), PPS (revacc. follow-up phase)	Visit 3 – Visit 4	Eliminate from Visit only
	Number of days between Visit 4 and Visit 5 blood sample is outside [25-90 days]	PPS (revacc. active phase), PPS (revacc. follow-up phase)	Visit 4 – Visit 5	Eliminate from Visit only
2100	Serological results not available or blood sample not enough (low volume, not sufficient to perform testing).	PPS (LTFU), PPS (revacc. active phase), PPS (revacc. follow-up phase)	Visit 1 – Visit 7 Note: only the timepoint of the missing result will be excluded. For example, if a subject is missing results from Visit 1, but has results from other timepoints, only the Visit 1 will be excluded, the results at the other timepoints will be presented.	Eliminate from Visit only
2120	Assessment not properly performed – Obvious incoherence or abnormality or error in data, or unreliable data as a result of confirmed sample mismatch or confirmed inappropriate sample handling (including temperature deviations of samples) at lab	PPS (LTFU), PPS (revacc. active phase), PPS (revacc. follow-up phase)	Visit 1 – Visit 7	Eliminate from Visit only
2500	Vaccinated but lower volume was given	PPS (revacc. active phase), PPS (revacc. follow-up phase)	Visit 3 - Visit 7	Eliminate from Visit and onwards

Prior to database lock, during data management review (DMR), it will be determined if an elimination code applies to all visits, a specific visit (timepoint) only, or a specific visit (timepoint) onwards.

The investigator should endeavour to have the subjects come in for the visits within the protocol defined intervals, however, subjects may not be excluded from the PPS for Immunogenicity after revaccination course if they make the study visit outside these intervals. The intervals between study visits may not match the protocol defined and amended time windows due to special circumstances in which case, at the discretion of the sponsor, the

intervals may be extended to the below intervals for analysis. These new windows will be used in determining PPS elimination as part of code 2090.

Visit	Original Protocol Defined Intervals	Amended Protocol Intervals allowed during special circumstances (e.g., COVID-19 pandemic)	Intervals allowed for statistical analysis
Visit 1 – Visit 2	[330-415 days]	
Target: [180-540 days]
 
The start of the interval may be moved by up to 6 months (starting no later than 18 months post-Visit 1)
	Any interval as informative for LTFU
Visit 1 – Visit 3	[690-775 days]	
The start of the interval may be moved by up to 6 months (starting no later than 30 months post-Visit 1), e.g., to avoid potential seasonal recurrence of COVID-19.
 
[510-985 days]
 
For delayed enrolled subjects, there is no strict interval. Ideally, there would be at least 6 months between their combined Visit 1/Visit 2 and Visit 3, but this is not required. The latest timepoint for Visit 3 to occur for delayed enrolled subjects would match the latest timepoint of all other previously enrolled subjects' Visit 3 so that all subjects can be revaccinated contemporaneously. The goal is to maintain similar revaccination follow-up
	Any interval as informative for LTFU

		timing so as not to delay study end.	
Visit 3 – Visit 4	[30-60 days]	[30-182 days]	[25-90* days]
Visit 4 – Visit 5	[30-48 days]	[30-90 days]	[25-90* days]
Visit 4 – Visit 6	[330-415 days]	[330-445 days] The allowed interval for Visits 6 should be the same for both the re-vaccinated and non-revaccinated subjects.	Any interval as informative for LTFU
Visit 4 – Visit 7	[690-775 days]	[690-805 days] Visit 7 may be Scheduled earlier to make up for delays incurred during times of special circumstance, in order to maintain planned duration of the study. Delayed or cancelled if special circumstances preclude the original planned visit. The allowed interval for Visit 7 should be the same for both the re-vaccinated and non-revaccinated subjects.	Any interval as informative for LTFU

Additionally, out-of-window visits are expected due to COVID-19 pandemic issues that do not fall into the “special circumstances” as just described, e.g., reduced clinic hours or patient capacity, but not the “clinics closed” requirement to enact special circumstances provisions. Determination of elimination, or not, for these out-of-window visits will take place during DMR pre-analysis.

Official elimination will take place during DMR in the pre-analysis meeting as the intervals for PPS eligibility may need to be adjusted or expanded further as the goal is to get as much immunogenicity and LTFU data as possible in this small sample size.

